## 6. ADVERSE EVENTS:

### 6.1 Known Adverse Events and Mitigation Strategy

Adapted from Micromedex

- \* Cardiovascular: Congestive heart failure, Edema
- \* Dermatologic: Angioedema
- \* Endocrine metabolic: Diabetes mellitus exacerbation, weight gain
- \* GI: Abdominal discomfort, tooth disorder
- \* Hematologic: Anemia, decreased hemoglobin
- \* Hepatic: Hepatotoxicity, liver failure
- \* Musculoskeletal: Fracture of bone, myalgia, osteopenia
- \* Neurologic: Headache, paresthesia
- \* Ophthalmic: Diabetic macular edema, retinopathy
- \* Renal: Malignant tumor of urinary bladder
- \* Reproductive: Ovulation in premenopausal anovulatory women
- \* Respiratory: Dyspnea, pharyngitis, sinusitis, upper respiratory infection

The ACTOS (pioglitazone hydrochloride) prescribing information contains the following information. The same side effect profile is expected in all generic equivalents.

In monotherapy studies, edema was reported for 4.8% (with doses from 7.5 mg to 45 mg) of patients treated with pioglitazone versus 1.2% of placebo-treated patients.

Placebo-Controlled Clinical Studies of pioglitazone Monotherapy: Adverse Events Reported at a Frequency >5% of Patients Treated with pioglitazone(% of Patients) the following:

	Placebo N=259	pioglitazone N=606
Upper Resp. Tract Infection	8.5	13.2
Headache	6.9	9.1
Sinusitis	4.6	6.3
Myalgia	2.7	5.4
Tooth Disorder	2.3	5.3
Diabetes Mellitus Aggravated	8.1	5.1
Pharyngitis	0.8	5.1

These known risks are the basis for several inclusion exclusion criteria.

**Per the current Black Box Warning, patients will be strictly monitored for signs and**

**symptoms of heart failure. They will report weight gain, new edema, and new dyspnea immediately to the study site.**

All subjects will be given the ACTOS(pioglitazone) Medication Guide as recommended in the 9/2009 REMS. Please see Appendix E.

## 6.2 Adverse Event Reporting

- **CTCAE term (AE description) and grade:** The descriptions and grading scales found in the revised NCI Common Terminology Criteria for Adverse Events (CTCAE) version 4.0 will be utilized for AE reporting, available for download from the CTEP web site (<http://ctep.cancer.gov>).
- **“Expectedness”:** All AEs will be designated as ‘Unexpected’ or ‘Expected’
- **Attribution** of the AE will be designated in this manner:
  - Definite – The AE is *clearly related* to the study treatment.
  - Probable – The AE is *likely related* to the study treatment.
  - Possible – The AE *may be related* to the study treatment.
  - Unlikely – The AE is *doubtfully related* to the study treatment.
  - Unrelated – The AE is *clearly NOT related* to the study treatment.

## 6.3 Data and Safety Monitoring

6.3.1 Scheduled meetings by the study specific Data and Safety Monitoring Committee (DSMC) will occur quarterly or more frequently depending on the activity of the protocol. This committee will include the protocol investigators, data manager or designee, and other members of the study team involved with the conduct of the trial.

6.3.2 During these regular meetings, the DSMC will discuss matters related to:

1. safety of study participants (SAE/UaP reporting)
2. validity and integrity of the data
3. enrollment rate relative to expectations, characteristics of participants, retention of participants, adherence to protocol (potential or real protocol deviations)
5. data completeness

6.3.3 DSMC meetings will be documented by the Protocol Specific Data and Safety Monitoring Report (DSMR). The data manager or designee assigned to the trial will be responsible for completing the report. DSMRs will be signed by the Principal Investigator or by one of the co-investigators and will be kept on file in the study record.

6.3.4 The University of Michigan Comprehensive Cancer Center Data and Safety Monitoring Board (UMCCC DSMB) will provide independent oversight of the safety and data integrity for this trial. DSMRs and any other pertinent documents will be submitted to the UMCCC DSMB for review on a quarterly basis unless specified more frequently by a DSMB ruling.

6.3.5 The Principal Investigator or designee will forward all correspondence and recommendations generated by the UMCCC DSMB to the Institutional Review Board.

## **6.4 Pregnancy**

Any pregnancy must be reported to the Principal Investigator at the Coordinating Center in the same manner as a Serious Adverse Event. A subject who becomes pregnant shall be removed from study treatment. All pregnancies will be followed until outcome can be reported.

# **7. CORRELATIVE/SPECIAL STUDIES**

## **7.1 Laboratory Correlative Studies**

Detection of the PAX8-PPARgamma fusion gene.

Eligibility requires that the tumor contain the PAX8-PPARgamma fusion gene. This will be assessed in specimens of the resected primary tumor or metastases obtained from all participating patients. Please see supplemental Lab Manual for procedures.

Optional MRI evaluation of tumor lipid.

Since pioglitazone induces lipid accumulation in the thyroids of the mouse model, we predict that pioglitazone will induce lipid accumulation in the metastases of patients. For patients who consent, tumor lipid content will be evaluated by MRI at baseline (any time after informed consent and before the first dose of pioglitazone), and at 24±1 weeks or the end of treatment, whichever comes first.

Optional fresh biopsy of metastasis.

For patients with biopsy-accessible metastases that meet RECIST criteria for measurable disease, optional fresh biopsies of the metastases may be obtained. Institutional procedures for procurement of fresh tumor biopsies will be followed. Biopsies should be obtained pretreatment (anytime after informed consent and before the first dose of pioglitazone) and also may be obtained within 1 day of the last treatment. The biopsy specimens will be analyzed for the PAX8-PPARgamma fusion gene per above, and will be stored for potential future analyses of biomarkers that may correlate with response to or lack of response to pioglitazone. For example, the expression of PPARgamma target genes may be analyzed.

Optional collection of sera.

For patients who consent, serum (up to 21 mL) may be collected pretreatment (anytime after informed consent and before the first dose of pioglitazone) and also may be collected within one day of the last treatment. Sera will be stored at -80C for potential future analysis of biomarkers that may correlate with response to or lack of response to pioglitazone.

Optional collection of peripheral blood DNA

For patients who consent, peripheral venous blood (up to 7 mL) will be collected for the isolation of DNA and the determination of DNA sequence. This may be compared to DNA extracted from the primary tumor or metastases to identify gene mutations or polymorphisms that may correlate with the development of the cancer and its response or lack thereof to pioglitazone.

Optional radioiodine scan and potential radioiodine therapy at the end of pioglitazone therapy.

This will be addressed in a separate follow-up protocol available to subjects completing this study.

## **8. MEASUREMENT OF EFFECT**

### **8.1 Antitumor Effect – Solid Tumors**

For the purposes of this study, patients should be re-evaluated for response every 12 ±1 weeks, with a confirmatory CT 4 or more weeks after the 24 week imaging if required by RECIST criteria.

Response and progression will be evaluated in this study using Response Evaluation Criteria in Solid Tumors (RECIST) 1.1.

#### **8.1.1 Definitions**

Evaluable for toxicity. All patients will be evaluable for toxicity from the time of their first treatment with pioglitazone.

Evaluable for objective response. Only those patients who have measurable disease present at baseline (an eligibility criterion), have received at least 11 weeks of therapy and have had their disease re-evaluated; or who come off therapy due to progressive disease or unacceptable adverse events at any time, will be considered evaluable for response. These patients will have their response classified according to the definitions stated below.

### **8.2 Response Criteria (using tumor related imaging CT)**

#### **8.2.1 Evaluation of Target Lesions**

Complete Response (CR): Disappearance of all target lesions

Partial Response (PR): At least a 30% decrease in the sum of the longest diameter (LD) of target lesions, taking as reference the baseline sum LD

Progressive Disease (PD): At least a 20% increase in the sum of the LD of target lesions, taking as reference the

		smallest sum LD recorded since the treatment started or the appearance of one or more new lesions
Stable Disease (SD):		Neither sufficient shrinkage to qualify for PR nor sufficient increase to qualify for PD, taking as reference the smallest sum LD since the treatment started
8.2.2 Evaluation of Non-Target Lesions		
Complete Response (CR):	Disappearance of all non-target lesions and serum tumor marker (thyroglobulin) level $\leq 0.5$ ng/mL	
Incomplete Response/ Stable Disease (SD):	Persistence of one or more non-target lesion(s) and/or serum tumor marker (thyroglobulin) level $> 0.5$ ng/mL	
Progressive Disease (PD):	Appearance of one or more new lesions and/or unequivocal progression of existing non-target lesions	

Although a clear progression of “non-target” lesions only is exceptional, the opinion of the treating physician should prevail in such circumstances, and the progression status should be confirmed at a later time by the review panel (or Principal Investigator).

### **8.2.3 Evaluation of Best Overall Response**

The best overall response is the best response recorded from the start of the treatment until disease progression/recurrence (taking as reference for progressive disease the smallest measurements recorded since the treatment started). The patient's best response assignment will depend on the achievement of both measurement and confirmation criteria.

Target Lesions	Non-Target Lesions	New Lesions	Overall Response	Best Response for this Category Also Requires:
CR	CR	No	CR	>4 wks. confirmation
CR	Non-CR/Non-PD	No	PR	>4 wks. confirmation
PR	Non-PD	No	PR	
SD	Non-PD	No	SD	documented at least once >4 wks. from baseline

PD	Any	Yes or No	PD	no prior SD, PR or CR
Any	PD*	Yes or No	PD	
Any	Any	Yes	PD	

\* In exceptional circumstances, unequivocal progression in non-target lesions may be accepted as disease progression.

Note: Patients with a global deterioration of health status requiring discontinuation of treatment without objective evidence of disease progression at that time should be reported as "*symptomatic deterioration*". Every effort should be made to document the objective progression even after discontinuation of treatment.

### 8.3 Other Response Parameters

Serum thyroglobulin will be reviewed for the 12 months prior to enrollment, and will be obtained at enrollment and at  $12\pm 1$  and  $24\pm 1$  weeks of therapy. The changes in thyroglobulin before pioglitazone treatment and after treatment will be summarized overall and by response. Serum thyroglobulin will not be used as a response parameter if endogenous antibodies invalidate the measurement.

Optional correlative study. MRI will be used to assess lipid content of target lesions pre-study, and at  $24\pm 1$  weeks or the end of treatment, whichever comes first. The changes in lipid content after treatment will be summarized overall and by response.

## 9. STATISTICAL CONSIDERATIONS

### 9.1 Study Design

This is a phase II study with a primary endpoint of response (CR or PR per RECIST criteria) to pioglitazone therapy. Best response during the 24 weeks on Pioglitazone therapy will be assessed in thyroid cancer patients with metastatic disease who have CT evidence of disease progression in the prior 14 months. It is expected that without treatment there would be no improvement in the disease in these patients. This drug will be of interest to pursue alone or in combination with other therapies with a 40% best response rate. Accrual of 14 evaluable patients at a 95% two-sided significance level will provide 87% power to detect a 40% response rate compared to the expected 5% or less. A patient will be evaluable if they remain on treatment for 11 weeks or they are removed from study due to progression or toxicity.

Secondary endpoints include toxicity, serial measurements of serum thyroglobulin, lipid content of metastases determined by MRI, and radioiodine uptake. Since this drug is well known and used in humans we do not expect toxicity to be a problem. However, toxicity will be observed and reported throughout the trial as this is the first trial with Pioglitazone in this patient population.

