#### **4.3 Duration of Therapy**

Subjects will continue treatment for 28 weeks unless one of the following applies;

- Progressive Disease per RECIST criteria at any time
- Stable Disease per RECIST at 24 weeks
- Best Response per RECIST at 12 weeks and confirmed at 24 weeks
- Intercurrent illness that prevents further administration of treatment
- Unacceptable adverse events
- Patient decides to withdraw from the study
- General or specific changes in the patient's condition render the patient unacceptable for further treatment in the judgment of the investigator.

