#### 4.7 Study Calendar

	Pre-Study	Day 1	Wk 2	Wk 4	Wk 6	Wk 8	Wk 10	Wk 12	Wk 14	Wk 16	Wk 18	Wk 20	Wk 24/ EOT	Wk 28	Post treatment
Pioglitazone a		X													
Informed consent	X														
Demographics	X														
Medical history	X														
Concurrent meds	X														
Physical exam	X							X					X		
Vital signs	X							X					X		
Height	X														
Weight b															
Performance status	X							X					X		
Serum chemistry cd	X	X g				X				X			X		
CBC d	X	X g				X				X			X		
Thyroid blood tests de	X	X g					X						X		
β-hCG df	X														
Adverse event evaluation h	X		X	X				X			X		X		X
Tumor related imaging i	X							X					X	X	
Other correlative studies j	X												X		

a: Dose per protocol; orally administered once daily for 24-28 weeks..

b: Weight obtained at each study site visit and once/week on each subject's same home scale.

c: Pre-Study and Day 1 chemistries: bicarbonate, BUN, chloride, creatinine, glucose, potassium, SGOT[AST], sodium. At weeks 8, 16, 24: glucose, AST.

d: Blood tests can be performed locally.

e: TSH, Free T4, thyroglobulin, thyroglobulin antibodies. All thyroglobulin measurements are to be performed in the same laboratory. Serum thyroglobulin will not be used as a response parameter if endogenous antibodies invalidate the measurement.

f: Pregnancy test in women of childbearing potential only.

g: Within 1 month prior to administration of protocol therapy. Pre-Study assessments if within 1 month will suffice.

h: Adverse events evaluations at weeks 2, 4, 18 and post treatment (within 4 weeks and at 6 months) will be by telephone.

i: Baseline CT or MRI scans must be done within 4 weeks prior to the start of therapy. Baseline CT includes neck, chest and abdomen. Follow-up imaging for disease response is at sites of disease detected at baseline and must include abdomen in cases of elevated AST to evaluate for liver metastases. Week 28 confirmatory CT for patients who need such for RECIST criteria confirmation. Baseline MRI includes: areas with lesions on CT for which there is reasonable diagnostic uncertainty that may be clarified by MRI; and/or brain if clinically indicated.

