j: Optional correlative studies at Pre-Study and within 1 day of final dose of pioglitazone. Baseline optional tumor lipid MRI includes areas of measurable disease. Follow-up tumor lipid MRI to be at sites of quantifiable tumor lipid at baseline, and is done at week 24 or end of treatment, whichever comes first.

k: All visits beyond day 1 shall occur at their designated timepoint  $\pm$  5 days.

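### The week-28 confirmatory CT can sit inside its calendar window yet miss the four-week minimum in 8.1, and 9.1 and 9.2 do not say whether a week-24 response confirmed later counts

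*Combined protocol and SAP*

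**What the plan says.** **Period for best response.** Section 9.1: "Best response during the 24 weeks on Pioglitazone therapy will be assessed in thyroid cancer patients with metastatic disease". Section 8.2.3 sets a different end: "The best overall response is the best response recorded from the start of the treatment until disease progression/recurrence". Section 9.2 counts a CR or PR reached during treatment.

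**Confirmation.** Section 8.2.3: "The patient's best response assignment will depend on the achievement of both measurement and confirmation criteria". In its table, the two rows with a complete response of the target lesions carry the entry ">4 wks. confirmation". The cell for an ordinary partial response is blank in the text available.

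**Timing of the confirming scan.** Section 8.1 schedules response imaging every 12 ±1 weeks, "with a confirmatory CT 4 or more weeks after the 24 week imaging if required by RECIST criteria". Section 4.7, footnote i: "Week 28 confirmatory CT for patients who need such for RECIST criteria confirmation". Footnote k: "All visits beyond day 1 shall occur at their designated timepoint", with a tolerance of ±5 days and no exception for this CT.

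**Length of treatment.** Section 4.3: "Subjects will continue treatment for 28 weeks unless one of the following applies". The listed exceptions include stable disease at week 24 and a week-12 response confirmed at week 24. Footnote a gives a range of 24 to 28 weeks. Section 2.2 gives 24 weeks.

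**The concern.** A response first seen at week 12 can be confirmed at week 24, inside every period the plan names. A response first seen at week 24 cannot. Its confirming scan comes about four weeks later, outside the 24 weeks in 9.1 and close to, or past, the last dose.

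Two things can then go wrong. A site that follows the calendar can scan too early for 8.1, leaving a confirmation that does not qualify. Or a valid scan can fall after treatment has ended, and the statistical section gives no rule for whether it counts. In a trial this small, the status of one late response should not be left open until the data are seen.

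**Working it through.** **Inputs.** I take week *n* as day 7*n*, so week 24 is day 168 and week 28 is day 196 (a one-day shift in numbering leaves the gaps unchanged). Tolerance is ±5 days at each visit (footnote k) or ±1 week for the response scan (8.1). The minimum gap is 28 days (8.1). Treatment lasts up to 28 weeks (4.3). There are 14 evaluable patients in 9.1 and 15 in 9.3, with response rates of 5% and 40% (9.1).

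**1. The plan's own figure.** For an exact binomial test with n = 14 and an upper tail of at most 0.025:
- P(X ≥ 3 | 5%) = 0.0301, too large.
- P(X ≥ 4 | 5%) = 0.0042, so the rule is at least 4 responders.
- Power is P(X ≥ 4 | 40%) = 0.876, which agrees with the stated 87%.

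**2. Gap between the two scans under footnote k.** Let d24 and d28 be the deviations in days, each from −5 to +5. Then gap = 28 + d28 − d24.
- Shortest: 28 − 5 − 5 = 18 days. Longest: 28 + 5 + 5 = 38 days.
- With the week-24 scan on its nominal day: 23 to 33 days.
- The gap reaches 28 days only if d28 ≥ d24. Of 11 × 11 = 121 permitted date pairs, 66 satisfy this and 55 do not. This counts permitted dates and is not a probability.
- The number of compliant week-28 days is 11 when d24 = −5, 6 when d24 = 0, and 1 when d24 = +5.

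**3. Earliest valid confirmation against the end of treatment.** Earliest valid day = day of week-24 scan + 28.

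| Week-24 scan | Earliest valid confirmation | Position |
|---|---|---|
| Day 163 to 168 | Day 191 to 196 | Within 28 weeks of treatment |
| Day 169 to 173 | Day 197 to 201 | After 28 weeks (day 196), still in footnote k's week-28 window |
| Day 174 to 175 (allowed by 8.1 only) | Day 202 to 203 | Outside footnote k's week-28 window (day 191 to 201) |

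In the last row no date meets both 8.1 and footnote k. With the scan on day 175, the shortest gap the calendar allows is 191 − 175 = 16 days.

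**4. What one response can decide.** Section 9.2 reports a 95% binomial interval. I assume the exact (Clopper-Pearson) form and a comparison with the 5% reference rate in 9.1:
- 3/14: 4.66% to 50.8%. 4/14: 8.39% to 58.1%.
- 3/15: 4.33% to 48.1%. 4/15: 7.79% to 55.1%.

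With either number of patients, three responders leave 5% inside the interval and four exclude it. This is the same cut-off as in step 1.

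**The case against.** The best defence is that 9.1 says when a response must be seen, and confirmation is a separate later step. Section 8.2.3 does separate measurement from confirmation, and 8.1 and footnote i both provide the later scan. The exceptions in 4.3 leave mainly first responders at week 24 on treatment to week 28, which would serve little purpose if their responses could not count. This reading is coherent and probably intended. What remains is that 9.1 and 9.2 do not state it and end the period at different points.

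A reader might infer that 9.1 excludes every response first seen at week 24, and that power falls accordingly. The documents do not support that. It needs the strictest reading of 9.1, against the sections just named, and a share of responses first appearing at week 24 that is given nowhere.

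A reader might also infer that the calendar forces early scans. It does not: under footnote k alone, at least one compliant day always exists, and a CT done too early would breach 8.1. The window permits the error without requiring it. Only a week-24 scan on day 174 or 175 leaves no compliant date.

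Nor do the treatment-length passages all conflict. Footnote a's range is what 4.3 produces once its week-24 exceptions apply; only 2.2 differs.

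The reach may also be small. If the blank cell for an ordinary partial response is intended, only responses with complete disappearance of the target lesions need confirmation. Even those meet the 30% shrinkage measure for a partial response, so CR-or-PR status might not change. That limit stands. Finally, the decisive role of the fourth responder holds for any classification question at this sample size; it shows why a clear rule is needed, and does not measure this gap.

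**Conclusion.** The point holds as a minor one. Confidence is high that the wording and windows conflict, and moderate that the primary endpoint would be affected.

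- A confirmatory CT can respect the calendar and fail 8.1, with a gap as short as 18 days against the 28 required.
- With a week-24 scan on day 169 to 173, the first valid confirmation falls after 28 weeks of treatment. That is outside the 24 weeks of 9.1 and arguably outside the on-treatment condition of 9.2.
- With a scan on day 174 or 175, which 8.1 allows, 8.1 and footnote k cannot both be met.

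If the blank cell is a loss in reading the table, every response first seen at week 24 is affected; if not, only those with complete response of the target lesions. Sections 8.1 and 8.2.3 also differ at exactly 28 days, though the sign before the interval in 8.2.3 may be a reading error as well. The stated power is not in question and no loss of power is claimed.

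**What to change.** 1. **Scan windows.** In footnote k, exempt the confirmatory CT from ±5 days. Give it a one-sided window opening 28 days after the actual week-24 scan, with an upper limit set by the sponsor. Use one tolerance for the week-24 scan in both 8.1 and footnote k.
2. **Endpoint rule.** In 9.1 and 9.2, state that a CR or PR first documented on any scan up to and including week 24 counts when confirmed, where 8.2.3 requires it, at least 28 days later. Say that the week-28 CT qualifies even if it falls after the last dose. This is an endpoint decision, so it should be made before the data are seen. State also how a response that is unconfirmed, or confirmed too early, is classified.
3. **Table.** Use the same interval wording in 8.1 and 8.2.3, and check whether the blank partial-response cell is intended.
4. **Treatment length.** The sponsor must reconcile 2.2 with 4.3 and footnote a. No view is taken here on which is right.

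The cost is wording only. No scan is added, and some confirmatory CTs would fall a few days later.

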### 9.2 Analysis Plan

All CT and MRI scans will be reviewed centrally through the University of Michigan Department of Radiology. The primary endpoint analysis will report the best response percent and corresponding 95% binomial confidence interval. Only those patients who have measurable disease present at baseline (an eligibility criterion), have received at least 11 weeks of therapy and have had their disease re-evaluated; or who come off therapy due to progressive disease or unacceptable adverse events at any time, will be considered evaluable for response. Each evaluable patient will be assigned one of the following categories: 1) complete response, 2) partial response, 3) stable disease, 4) progressive disease, 5) early death from malignant disease, 6) early death from toxicity, 7) early death because of other cause, or 8) unknown (not assessable, insufficient data). All of the patients who met the evaluability criteria will be included in the analysis of the primary endpoint. Patients in response categories 1-2 while on treatment will be considered responders to treatment. Thus, an incorrect treatment schedule or drug administration does not result in exclusion from the analysis of the response rate.

All patients enrolled and who receive any drug will be assessable for toxicity from the time of their first treatment with study drug. Toxicity will be described by grade and type using frequencies and percentages.

Serum thyroglobulin will be reviewed for the 12 months prior to enrollment, and will be obtained at enrollment and at  $12\pm 1$  and  $24\pm 1$  weeks of therapy. The changes in thyroglobulin before pioglitazone treatment and after treatment will be summarized overall and by response. Patient profile plots will be created to descriptively show the serum thyroglobulin values over time. Means and standard deviations or medians and minimum and maximums will be used to summarize all patients at each time and changes from baseline at the later times. Similarly, statistical descriptions of the response group and the non-response groups will be reported.

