### **9.3 Sample Size/Accrual Rate**

We will accrue 15 evaluable patients, which allows for one drop out while still achieving the target enrollment of 14 patients. We expect to accrue ~4-5 patients per

year, for a total study accrual period of ~4 years.

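### Does Section 9.1 set two success bars, an observed 40% and the lower one behind its 87% power?

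*Combined protocol and SAP*

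**What the plan says.** Section 9.1 (Study Design) defines the primary endpoint as complete or partial response by RECIST. It gives one sentence on when the drug would merit further work: "This drug will be of interest to pursue alone or in combination with other therapies with a 40% best response rate". The sample-size statement comes next: "Accrual of 14 evaluable patients at a 95% two-sided significance level will provide 87% power to detect a 40% response rate". The null rate in that statement is at most 5%.

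Section 9.2 (Analysis Plan) describes the primary analysis as estimation: "The primary endpoint analysis will report the best response percent and corresponding 95% binomial confidence interval". It does not name the interval method or say what the interval is compared with.

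Section 9.3 (Sample Size/Accrual Rate) gives numbers only: "We will accrue 15 evaluable patients, which allows for one drop out while still achieving the target enrollment of 14 patients".

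None of these sections states a minimum number of responders, and none says whether 40% is a true or an observed rate.

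**The concern.** A reader who looks for the success criterion finds two candidates in Section 9.1. One is the sentence on a 40% response rate, worded much like the percentage that Section 9.2 will report. The other is the test implied by the power statement, which is met well below an observed 40%.

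If both were live, a result of 4 or 5 responders of 14 could be called a success because 5% is excluded, or a failure because 40% was not reached, and either author could cite Section 9.1. Such a result would not be rare. If the observed 40% were the intended bar, the trial would also have much less power than the 87% stated.

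**Working it through.** **Inputs.** From Section 9.1: n = 14 evaluable, null rate 5%, alternative 40%, two-sided level, power 87%. The 95% level is read as a two-sided type I error of 0.05, with 0.025 in the upper tail. From Section 9.3: n may reach 15.

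**Formulas.** For a rule of at least r responders, type I error is P(X ≥ r) with X ~ Binomial(n, 0.05), and power is P(X ≥ r) with X ~ Binomial(n, 0.40). Intervals are two-sided 95% Clopper-Pearson.

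**Step 1: reproduce the 87%.** At n = 14 and a true rate of 40%, the probabilities of 0, 1, 2 and 3 responders are 0.0008, 0.0073, 0.0317 and 0.0845, which sum to 0.1243. Power for at least 4 is 1 − 0.1243 = 0.8757.

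| n | Rule | Observed rate at the cut-off | Type I error at 5% | Power at 40% | 95% interval at the cut-off |
|---|---|---|---|---|---|
| 14 | ≥3 | 21.4% | 3.0% | 96.0% | 4.7% to 50.8% |
| 14 | ≥4 | 28.6% | 0.42% | 87.6% | 8.4% to 58.1% |
| 14 | ≥5 | 35.7% | 0.04% | 72.1% | 12.8% to 64.9% |
| 14 | ≥6 | 42.9% | 0.003% | 51.4% | 17.7% to 71.1% |
| 15 | ≥4 | 26.7% | 0.55% | 90.9% | 7.8% to 55.1% |
| 15 | ≥6 | 40.0% | 0.005% | 59.7% | 16.3% to 67.7% |

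With 0.025 in the upper tail, 3 responders are too few (3.0%) and 4 are enough (0.42%). Only the rule of at least 4 matches the stated power at n = 14. Two-sided approximations do not: 96.4% (normal, null variance), 76.2% (Wald) and 93.0% (arcsine).

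**Step 2: size of the supposed conflict.** The smallest count with an observed rate of at least 40% is 6, for either n. The chance of exactly 4 or 5 of 14 at a true 40% is 87.6% − 51.4% = 36.2%; it is 43% at a true 30% and 26% at a true 20%. With 15 patients the three figures are 31%, 42% and 29%.

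**Step 3: which reading fits.** The sentence of interest and the power sentence are adjacent and use the same 40%. The first explains why that rate was chosen and the second powers the trial for it. Power is always stated at a true rate. A rule of at least 6 of 14 would have type I error of about 0.003% and power of 51.4%, which does not fit a design presented as two-sided 5% with 87% power. The stated power is therefore evidence against the observed-rate reading. The term best response is simply the endpoint's name in Sections 8.2.3 and 9.1, so its recurrence in Section 9.2 does not make 40% a sample threshold.

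**Step 4: can Section 9.2 be applied as written?** Yes. The 95% interval corresponds to the 95% two-sided level of Section 9.1, and the null is given as 5%. The exact interval separates 3 of 14 (lower limit 4.7%) from 4 of 14 (8.4%), which is the rule recovered in step 1. That the intervals at 4 and 5 responders include 40% is not informative: at n = 14 the interval includes 40% for every count from 2 (1.8% to 42.8%) to 9 (35.1% to 87.2%).

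**The case for a change.** The best argument for a change is that Section 9.1 describes a test, with a null, an alternative, a level and power, so its rule ought to be written down before results are known. The interval method is also unnamed, and it matters next to the cut-off. At 3 of 14 the Wilson lower limit is 7.6% against 4.7% for Clopper-Pearson. At 4 of 14 the Wald lower limit is 4.9% against 8.4%. Two or three sentences would settle both points at no cost to patients or data.

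The omission is real. But the stated power already selects the method. At n = 14, comparing the lower limit with 5% requires at least 3 responders under Wilson (power 96.0%), at least 5 under Wald (72.1%) and at least 4 under Clopper-Pearson (87.6%). Only the last agrees with 87%. An analyst who works back from Section 9.1 reaches the exact interval and the cut-off of 4.

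The claim that power is overstated by about 36 points does not stand. It needs a rule of at least 6 of 14, which the documents do not contain.

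**Conclusion.** No change follows. This is missing detail that an analyst fills sensibly from the plan's own figures. The 87% is correct (87.6% exactly), the 40% is most naturally the assumed true rate, and the single bar is exclusion of 5%, met with at least 4 responders of 14 or of 15 (power 87.6% or 90.9%; type I error 0.42% or 0.55%).

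Little else hangs on the point. The trial is a single-arm phase II study, the plan describes no interim decision that uses the cut-off, and no patient's treatment depends on it. Readers will see the count and its interval whichever label is attached.

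The conclusion assumes that 40% is the design alternative and that the two-sided 5% is split evenly between the tails. If the sponsor did mean an observed 40%, power at a true 40% would be 51.4% with 14 patients or 59.7% with 15, but nothing in the documents says so.
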